#### **10.1.6 Follow-up (Visit 5, [Day 90 +/- 15 days])**

The Follow-up Visit (Visit 5) will take place at Day 90 ( $\pm$  15 days). The following procedures will be performed at the Follow-up Visit:

- Record any AEs that have occurred since the last visit and any changes in concomitant medication.
- Perform otoscopy, standard pure tone audiometry, extended high frequency audiometry, word recognition testing, WIN testing, and tympanometry.
- Record vital signs.

If the subject is not able to return to clinic for this visit due to any reason, a phone call visit will be performed. Any AEs and concomitant medication changes will be recorded.

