#### 7.1.6. Missing Data

Due to the exploratory nature of the study, no formal imputation on missing data will be performed. Missing data due to the COVID-19 pandemic will remain missing in the planned statistical summaries and analyses. Unless otherwise specified, incomplete data for the efficacy endpoints will be assumed missing at random (MAR) and analyzed using the MMRM approach.

For the WR and WIN, the number and percentage of subjects completing each word list at each visit will be summarized for treated ears by randomized treatment group for subjects in the FAS. For the audiometry endpoints, the number and percentage of subjects with non-missing, no response, or not done at each frequency and visit will be summarized for treated ears by randomized treatment group for subjects in the FAS.

Where recorded, visits impacted by the COVID-19 pandemic will be identified in data listings.

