#### 7.3.5. Improvement $\geq 10\%$ (5 words) in percentage of recognized words

- *Computation of the Endpoint*

Improvement  $\geq 10\%$  in percentage of recognized words at each post-baseline visit for treated ears will be computed as 1 if the absolute percent change from baseline in percentage of recognized words  $\geq 10\%$  and as 0, otherwise where absolute percent change from baseline is non-missing.

- *Analysis of the Endpoint*

The incidence of improvement  $\geq 10\%$  in percentage of recognized words at each post-baseline visit for treated ears will be summarized using frequencies and percentages by visit and treatment group for subjects in the FAS.

In treated ears only for subjects in the FAS, treatment group comparisons for incidence of improvement  $\geq 10\%$  in percentage of recognized words may be analyzed using a generalized estimating equation based on the binomial distribution with logit link. The fixed covariates may include treatment group, WR score at baseline ( $< 50\%$  versus  $\geq 50\%$ ), etiology of hearing loss (SSNHL versus NIHL), visit, and interaction between visit and treatment group. Covariates for WR score at baseline and etiology of hearing loss may be dropped if the model fails to converge. A random effect for within-subject, repeated measures variability may be included. The treatment group differences analyzed will be between each FX-322 group (including the pooled FX-322 group) versus placebo, and comparisons between the individual FX-322 groups (excluding the pooled FX-322 group). Odds ratios, 95% CIs, and p-values may be reported and comparisons will be made by visit and overall.

- *Sensitivity Analyses of the Endpoint*

The analyses will be repeated for subjects in the PPAS.

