### 7.5.2. AC and BC Improvement $\geq$ 10 dB from baseline for two contiguous frequencies

- *Computation of the Endpoint*

AC Improvement  $\geq$ 10 dB from baseline for two contiguous frequencies at each post-baseline visit for treated ears will be computed as 1 if the post-baseline threshold – baseline threshold is  $\geq$ 10 dB for two contiguous frequencies and as 0, otherwise. The endpoint will utilize imputed values per Section 7.5. The BC Improvement  $\geq$ 10 dB will be derived using the same approach.

- *Analysis of the Endpoint*

The incidence of AC improvement  $\geq 10$  dB from baseline for two contiguous frequencies at each post-baseline visit for treated ears will be summarized using frequencies and percentages by visit and treatment group for subjects in the FAS. The summary will be repeated for BC improvement.

In treated ears only for subjects in the FAS, treatment group comparisons for incidence of AC improvement  $\geq 10$  dB from baseline for two contiguous frequencies may be analyzed using a generalized estimating equation based on the binomial distribution with logit link. The fixed covariates may include treatment group, WR score at baseline (<50% versus  $\geq 50\%$ ), etiology of hearing loss (SSNHL versus NIHL), visit, and interaction between visit and treatment group. Covariates for WR score at baseline and etiology of hearing loss may be dropped if the model fails to converge. A random effect for within-subject, repeated measures variability may be included. The treatment group differences analyzed will be between each FX-322 group (including the pooled FX-322 group) versus placebo, and comparisons between the individual FX-322 groups (excluding the pooled FX-322 group). Odds ratios, 95% CIs, and p-values may be reported and comparisons will be made by visit and overall. The analysis will be repeated for BC improvement.

- *Sensitivity Analyses of the Endpoint*

The analyses will be repeated for subjects in the PPAS.

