### 7.5.3. AC and BC Improvement $\geq 15$ dB from baseline for any frequency

- *Computation of the Endpoint*

AC Improvement  $\geq 15$  dB from baseline for any frequency at each post-baseline visit for treated ears will be computed as 1 if the post-baseline threshold – baseline threshold is  $\geq 15$  dB for any frequency and as 0, otherwise. The endpoint will utilize imputed values per Section 7.5. The BC Improvement  $\geq 15$  dB will be derived using the same approach.

- *Analysis of the Endpoint*

The incidence of AC improvement  $\geq 15$  dB from baseline for any frequency at each post-baseline visit for treated ears will be summarized using the approach described in Section 7.5.2 for subjects in the FAS. The summary will be repeated for BC improvement.

Treatment group comparisons for AC improvement and BC improvement may be performed using the approach described in Section 7.5.2 for subjects in the FAS.

- *Sensitivity Analyses of the Endpoint*

The analyses will be repeated for subjects in the PPAS.

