### 7.5.9. Composite WR, WIN and Pure Tone Audiometry Endpoint

- *Computation of the Endpoint*

The composite endpoint will be assessed in treated ears and defined as simultaneously meeting both of the following conditions at any visit (Day 90 or 210):

- A post-baseline  $\geq 10\%$  WR improvement OR a  $\geq 10\%$  WIN improvement, and
- A post-baseline 10 dB improvement in 2 contiguous frequencies or a post-baseline 15 dB improvement in any frequency for AC thresholds

Post-baseline  $\geq 10\%$  WR improvement is defined in Section 7.3.5 and  $\geq 10\%$  WIN improvement is defined in Section 7.4.5. Post-baseline  $\geq 10$  dB improvement in 2 contiguous frequencies for AC thresholds is defined in Section 7.5.2 and post-baseline  $\geq 15$  dB in any frequency for AC thresholds is defined in Section 7.5.3.

The composite endpoint will be computed as 1 if both conditions are met in the treated ear at the same visit for any of the post-baseline visits (Day 90 and 210) and as 0, otherwise.

- *Analysis of the Endpoint*

The incidence of the composite WR, WIN and pure tone audiometry endpoint for treated ears will be summarized using frequencies and percentages by treatment group for subjects in the FAS.

In treated ears only for subjects in the FAS, treatment group comparisons for the composite endpoint will be analyzed using a logistic regression model. The fixed covariates will include treatment group, WR score at baseline ( $< 50\%$  versus  $\geq 50\%$ ), and etiology of hearing loss (SSNHL versus NIHL). The treatment group differences analyzed will be between each FX-322 group (including the pooled FX-322 group) versus placebo, and comparisons between the individual FX-322 groups (excluding the pooled FX-322 group). Odds ratios, their 95% CIs, and p-values will be reported.

- *Sensitivity Analyses of the Endpoint*

The analyses will be repeated for subjects in the PPAS.

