#### 7.6.6. Shift from no signal to any signal by frequency

- *Computation of the Endpoint*

For each frequency, shifts from no signal to any signal will be computed in subjects in the FAS with no signal (missing/imputed hearing response) at baseline in the treated ear. At each post-baseline visit, subjects with any signal (any non-missing/not imputed hearing response) in the treated ear will be flagged as 1 and as 0, otherwise. The endpoint will utilize imputed values per Section 7.6.

- *Analysis of the Endpoint*

For each frequency, the incidence of shifts from no signal at baseline to any signal at each post-baseline visit for treated ears will be summarized using frequencies and percentages by visit and treatment group for subjects with no signal at baseline in the FAS.

- *Sensitivity Analyses of the Endpoint*

The analyses will be repeated for subjects in the PPAS.

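### Audiometry responder and EHFA signal-shift rules omit the non-missing condition used for the speech responders, so ears or frequencies never tested can be scored, against the plan's own missing-data rules

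*SAP*

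**What the plan says.** SAP 7.5.2 scores a treated ear 1 at a post-baseline visit if the 10 dB criterion is met at two adjacent frequencies, and closes with "dB for two contiguous frequencies and as 0, otherwise. The endpoint will utilize imputed values per Section 7.5". SAP 7.5.3, for 15 dB at a single frequency, closes in the same way: "dB for any frequency and as 0, otherwise. The endpoint will utilize imputed values per Section 7.5". SAP 7.6.2 and 7.6.3 repeat both rules for EHFA, and 7.5.4 and 7.6.4 combine them. The air-conduction limb of the composite in 7.5.9 uses 7.5.2 and 7.5.3; the composite is 1 when both limbs are met "at the same visit for any of the post-baseline visits (Day 90 and 210) and as 0, otherwise". The imputation mentioned covers only a recorded no-response (NR) after Screening. Missing Screening values stay missing (7.5, 7.6).

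The word recognition (WR) responder in SAP 7.3.5 is worded differently: "and as 0, otherwise where absolute percent change from baseline is non-missing". The words-in-noise (WIN) responders in 7.4.5 and 7.4.7 carry equivalent conditions.

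The EHFA signal shifts (SAP 7.6.6 to 7.6.8) are taken in FAS subjects "with no signal (missing/imputed hearing response) at baseline in the treated ear" (by frequency, or for two or three adjacent frequencies). The later flag is 1 for any real, non-imputed response and 0 in every other case.

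Three general rules bear on this. SAP 7.1.6 plans no formal imputation and adds: "Missing data due to the COVID-19 pandemic will remain missing in the planned statistical summaries and analyses". SAP Section 3 puts missing categorical data in a separate row outside the percentages. Protocol 14.1.5 drops subjects without data from the descriptive calculation concerned.

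Protocol 10.1.6 says of Day 90: "If the subject is not able to return to clinic for this visit due to any reason, a phone call visit will be performed". Protocol 10.1.5 and 10.1.8 say the same of Days 60 and 150. These calls collect adverse events and medication changes, plus questionnaires at Day 60, but no audiometry.

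**The concern.** The SAP states the non-missing condition three times for speech responders and leaves it out of every audiometry responder. A programmer who follows the audiometry sentences as written will code an ear without an audiogram as not improved. One who follows the general rules will leave it missing. Both could claim to have followed the plan, and they would report different denominators and rates.

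Under the literal rule, audiometry responder rates fall as missed visits rise. If missed visits differ between arms, a difference appears without any drug effect. WR and audiometry responder rates at the same visit would also rest on different sets of ears.

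The EHFA signal shift has a problem of the opposite sign: a frequency skipped at Screening and heard later is counted as signal gained.

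**Working it through.** **1. The definitions side by side.**

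| SAP section | Endpoint | When 0 is assigned |
|---|---|---|
| 7.3.5, 7.4.5, 7.4.7 | WR and WIN responders | criterion not met and data present |
| 7.5.2, 7.5.3, 7.6.2, 7.6.3 | dB responders | all other cases |
| 7.5.9 | WR/WIN/audiometry composite | all other cases |
| 7.6.6 to 7.6.8 | EHFA signal shift | all other cases |

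**2. Can the audiogram be absent?** Yes, by at least three routes: phone replacement at Days 60, 90 and 150; early discontinuation, since the FAS needs only one dose; and single frequencies not done. A frequency coded NR at Screening also has no baseline threshold, so no change can be computed there.

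**3. Do the general rules settle it?** They favour leaving data missing, but not conclusively. The missing-at-random default in SAP 7.1.6 applies unless otherwise specified and works through MMRM, whereas these endpoints use GEE or logistic regression. The Missing row in Section 3 acts on missing values, and an endpoint already derived as 0 is no longer missing.

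**4. Size for a per-visit responder.** The plan has no figure to reproduce: the sample size has no formal basis, and no responder or missed-visit rate is given. All rates below are assumed. With true rate p and a share m of visits without an audiogram, unrelated to response, the expected reported rate is p(1 − m).

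- Equal missingness, true rates 40% versus 20% (difference 20 points; odds ratio (0.40/0.60)/(0.20/0.80) = 2.67):
  - m = 10%: 36% versus 18%, difference 18 points, odds ratio 2.56
  - m = 20%: 32% versus 16%, difference 16 points, odds ratio 2.47
  - m = 30%: 28% versus 14%, difference 14 points, odds ratio 2.39
- Unequal missingness, true rate 30% in both arms:
  - 10% missing on FX-322, 30% on placebo: 0.30 × 0.90 = 27% versus 0.30 × 0.70 = 21%, a spurious +6 points, odds ratio (0.27/0.73)/(0.21/0.79) = 1.39
  - the reverse: 21% versus 27%, −6 points, odds ratio 0.72

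With 24 ears per arm, each reclassified ear moves an arm's rate by about 1/24 = 4.2 points.

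**5. The composite.** It uses Days 90 and 210 only. Protocol 10.1.10 (Day 210) has no phone clause, so that route affects Day 90 alone, and at the final analysis a subject without Day 90 data can still score 1 at Day 210. The factor (1 − m) therefore does not carry over directly to the final composite. At the interim it can: SAP Section 10 includes the composite and excludes efficacy data after Day 90, so a missing Day 90 audiogram leaves no second chance.

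**6. EHFA baseline.** Section 7.6 imputes NR only after Screening. At baseline, then, missing/imputed can only mean missing, which covers both NR and not done. SAP 7.1.6 tabulates these as separate states, so the data can tell them apart. Let k ears be truly NR at baseline with true shift rate q, and let u ears be untested at Screening but audible later. The observed rate is (kq + u)/(k + u). With k = 12 and q = 0 (assumed):

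- u = 1: 1/13 = 7.7%
- u = 2: 2/14 = 14.3%
- u = 4: 4/16 = 25%

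Restricting the baseline group to coded NR gives 0% in each case.

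**The case against.** A reader might infer that the plan has adopted missing-equals-failure for audiometry. The documents do not support that. SAP 7.1.6, SAP Section 3 and Protocol 14.1.5 all lean towards leaving data missing, and SAP 7.1.2 lets early-termination and unscheduled efficacy data fill an empty visit. This part of the objection stands: for the responders it is an unresolved conflict, not a settled rule.

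The EHFA phrase may be shorthand for missing with an NR code, the sense used for post-Screening values. That is plausible, but the text does not say it. Screening calls for EHFA at all six frequencies, and nothing suggests that not-done results are common.

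The consequence is also limited. There is no primary endpoint, p-values are descriptive, and the GEE comparisons are optional. The protocol's named efficacy endpoints are mean changes, and the continuous threshold models are unaffected. Visit attendance and audiometry completeness are tabulated by arm, so heavy missingness would be visible. All arms receive four blinded injections, and nothing in the documents indicates that missed visits will differ by arm. The signal shifts are descriptive only, and EHFA is not in the interim list.

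These points lower the stakes but do not remove the defect. The responder percentages and the composite logistic model are firm commitments, and in an exploratory trial the reported rates are the result.

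**Conclusion.** The point holds as a wording error and an internal conflict. As written, the dB responders, the composite and the signal shifts assign 0 to ears that were not assessed, contrary to the plan's general rules and unlike its speech responders. For EHFA only, the baseline definition also admits untested frequencies as no-signal.

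The size cannot be estimated from the documents. The illustrations (14 to 18 points reported for a true 20 with 10% to 30% missing; ±6 points with no true difference when missingness is 10% in one arm and 30% in the other) rest on assumed rates and on missingness unrelated to response. Equal missingness only shrinks the contrast; a spurious difference needs unequal missingness. The composite is most exposed at the interim.

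The documents do not show that results will be biased for or against FX-322, that untested Screening frequencies are frequent, or that Day 210 can be replaced by a phone call.

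**What to change.** 1. **SAP 7.5.2, 7.5.3, 7.6.2, 7.6.3.** Score 1 if the criterion is met at assessed frequencies. Score 0 only where at least one frequency (for the two-frequency rule, one contiguous pair) has a computable change: a Screening value plus a post-baseline value, including an imputed post-baseline NR. Otherwise set to missing. Carry this into 7.5.4 and 7.6.4. Screening NR stays missing, so those frequencies contribute no dB change; in EHFA the signal-shift endpoints handle them.
2. **SAP 7.5.9.** Score 1 if both limbs are met at the same visit, 0 only if both limbs were assessable at one or more contributing visits (Day 90 only at the interim), and missing otherwise. A subject assessed at one visit only can still be scored 0, so add a sensitivity analysis at the final analysis restricted to subjects assessed at both visits.
3. **SAP 7.6.6 to 7.6.8.** Define baseline no-signal as a coded NR at Screening, exclude not done, and set the post-baseline flag only where the frequency was tested (a value or NR).

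While these sentences are being rewritten, check the direction of the subtraction in the dB responders. Post-baseline minus baseline of +10 dB or more is a worsening of a hearing threshold, so the score of 1 does not mean improved as the formula stands.

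The cost is SAP wording and derivation code, with slightly smaller denominators at visits with missing audiometry. It should be settled before unblinding, so that denominators are not chosen after results are seen.

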### 7.5.3. AC and BC Improvement $\geq 15$ dB from baseline for any frequency

- *Computation of the Endpoint*

AC Improvement  $\geq 15$  dB from baseline for any frequency at each post-baseline visit for treated ears will be computed as 1 if the post-baseline threshold – baseline threshold is  $\geq 15$  dB for any frequency and as 0, otherwise. The endpoint will utilize imputed values per Section 7.5. The BC Improvement  $\geq 15$  dB will be derived using the same approach.

- *Analysis of the Endpoint*

The incidence of AC improvement  $\geq 15$  dB from baseline for any frequency at each post-baseline visit for treated ears will be summarized using the approach described in Section 7.5.2 for subjects in the FAS. The summary will be repeated for BC improvement.

Treatment group comparisons for AC improvement and BC improvement may be performed using the approach described in Section 7.5.2 for subjects in the FAS.

- *Sensitivity Analyses of the Endpoint*

The analyses will be repeated for subjects in the PPAS.

#### 7.5.4. AC and BC Composite Improvement

- *Computation of the Endpoint*

The AC Composite Improvement endpoint is defined as the occurrence of either or both of the following conditions for a given subject's ear for a given visit: 1) AC Improvement  $\geq 10$  dB from baseline for two contiguous frequencies as described in Section 7.5.2 or 2) AC improvement  $\geq 15$  dB from baseline for any frequency as defined in Section 7.5.3. BC Composite Improvement is defined using the same approach.

- *Analysis of the Endpoint*

The incidence of AC Composite Improvement at each post-baseline visit for treated ears will be summarized using the approach described in Section 7.5.2 for subjects in the FAS. The summary will be repeated for BC Composite Improvement.

Treatment group comparisons for AC Composite Improvement and BC Composite Improvement may be performed using the approach described in Section 7.5.2 for subjects in the FAS.

- *Sensitivity Analyses of the Endpoint*

The analyses will be repeated for subjects in the PPAS.

#### 7.5.5. Mean overall PTA (AC over 0.5, 1, 2, and 4 kHz) and BCA (BC over 0.5, 1, 2 and 4 kHz)

- *Computation of the Endpoint*

At each visit and by ear (left, right), the mean overall PTA will be derived by averaging the AC audiometry dB hearing thresholds over 0.5, 1, 2, and 4 kHz frequencies. Left and right ears will be mapped to treated and untreated for analysis, as described in Section 3. Missing values will be imputed per Section 7.5. The BCA will be derived using the same approach. If hearing thresholds are missing for any of the 0.5, 1, 2, and 4 kHz frequencies (after imputation of records with classification of "NR"), PTA or BCA will be missing, respectively.

Mean overall PTA for each ear will be categorized into  $<26$ , 26-40, 41-55, 56-70, and  $>70$  for each visit and shifts from baseline to each post-baseline visit will be computed (e.g., 26-40 to 41-55).

- *Analysis of the Endpoint*

The mean overall PTA will be summarized descriptively for treated ears separately by visit and treatment group for subjects in the FAS. The summary will be repeated for BCA.

In treated ears only for subjects in the FAS, treatment group comparisons for mean overall PTA will be analyzed using a mixed-effect, repeated measures model using fixed covariates for treatment group, WR score at baseline ( $<50\%$  versus  $\geq 50\%$ ), etiology of hearing loss

(SSNHL versus NIHL), visit, and interaction between visit and treatment group. As described in Section 7.3.4, separate models will be fit specifying UN and AR(1) covariance structures (implemented with a repeated statement in SAS). The covariance structure providing the lowest corrected AICc and BIC values from the model will be implemented for the PTA and all other audiometry endpoints. The treatment group differences analyzed will be between each FX-322 group (including the pooled FX-322 group) versus placebo, and comparisons between the individual FX-322 groups (excluding the pooled FX-322 group). Comparisons will be made by visit (e.g., estimated LS Mean differences by visit) and overall (e.g., Type III Sums of Squares). The treatment group comparisons will also be performed for BCA.

The distribution in the shift in mean overall PTA categories for treated ears from baseline to each post-baseline visit will be summarized using frequencies and percentages by visit and treatment group for subjects in the FAS.

- *Sensitivity Analyses of the Endpoint*

The analyses will be repeated for subjects in the PPAS.

If there are any dosing administrations errors such that a not qualified ear is treated, the descriptive summaries by treated and untreated ears will be repeated for subjects in the FAS including all treated and untreated ear data.

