## **7.2 Endpoints**

### **Efficacy Endpoint(s)**

- Mean changes from Screening in:
  - Word Recognition in quiet (WR)
  - Words-In-Noise testing (WIN)
  - Standard Pure Tone Audiometry (air 0.25-8 kHz; bone 0.5-4 kHz)

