#### **14.1.5 Efficacy Exploration**

Efficacy endpoints will be summarized descriptively at each study timepoint including baseline. Calculations will include the observed data at each timepoint, and if relevant, the change from baseline. For continuous endpoints means, medians, standard deviations, minimums and maximum will be provided. For categorical endpoints the number and percent of subjects within each category will be calculated. Tabulations for selected endpoints will be presented by subgroups such as age, study site, duration of hearing loss, smoking status, and stratification factors used at randomization. Details will be provided in the SAP. For descriptive analyses, subjects with missing data will be excluded for a particular calculation.

For questionnaires, the analysis will follow the instructions for scoring and handling of missing data appropriate for the particular instrument.

Inferential statistical methods examining continuous endpoints will be examined via a Mixed Model for Repeated Measures (MMRM). Analyses will include pairwise contrasts and dose response. Inferential analyses for categorical endpoints will be analysed using univariate methods and/or Generalized Linear Mixed Models (GLMM). When appropriate, models will include adjustments for baseline as well as the stratification factors used at randomization. Departures of these models from the statistical assumptions will be assessed and alternative approaches maybe employed. Additionally, univariate models such as Analysis of Covariance and/or count models examining single timepoints of interest may also be examined. General methods for handling missing data for inferential analyses are described below (Section 14.2).

The inferential analyses will not be adjusted for multiple endpoints; however, for a given endpoint, adjusted p-values for pairwise comparisons to a control will be provided where

relevant along with the unadjusted p-values. Unadjusted 95% confidence intervals will also be provided. In some circumstances, adjusted confidence intervals may be calculated.

Efficacy endpoints will be analysed using the FAS. Further details regarding the exploratory analysis of efficacy will be outlined in the SAP.

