### 7.5.1. Air and Bone Conduction audiometry dB hearing thresholds by frequency

- *Computation of the Endpoint*

At each visit and by ear (left, right), the AC and BC audiometry dB hearing thresholds will be recorded for each frequency (Air: 0.25, 0.5, 1, 2, 3, 4, 6, and 8 kHz; Bone: 0.5, 1, 2, 3, and 4 kHz). Left and right ears will be mapped to treated and untreated for analysis, as described in Section 3. Missing values will be imputed per Section 7.5.

- *Analysis of the Endpoint*

Separately for AC and BC, the hearing threshold at each frequency will be summarized descriptively for treated and untreated ears separately by visit and treatment group for subjects in the FAS.

In treated ears only for subjects in the FAS, treatment group comparisons for AC hearing threshold at each frequency will be analyzed using separate mixed-effect, repeated measures models using fixed covariates for treatment group, WR score at baseline (<50% versus  $\geq$ 50%), etiology of hearing loss (SSNHL versus NIHL), visit, and interaction between visit and treatment group. The covariance structure (UN or AR(1)) that provides the best model fit for the PTA, as described in Section 7.5.5, will be implemented with a repeated statement in SAS. The treatment group differences analyzed will be between each FX-322 group (including the pooled FX-322 group) versus placebo, and comparisons between the individual FX-322 groups (excluding the pooled FX-322 group). Comparisons will be made by visit (e.g., estimated LS Mean differences by visit) and overall (e.g., Type III Sums of Squares) for each frequency. The analysis will be repeated for BC hearing thresholds.

A scatter plot of the mean AC audiometry thresholds by frequency will be prepared for treated and untreated ears for each treatment group with lines connecting each point.

- *Sensitivity Analyses of the Endpoint*

The analyses will be repeated for subjects in the PPAS.

If there are any dosing administrations errors such that a not qualified ear is treated, the descriptive summaries by treated and untreated ears will be repeated for subjects in the FAS including all treated and untreated ear data.

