### 7.6. Extended High Frequency Audiometry

EHFA will be performed to determine a subject's threshold dB for hearing at frequencies beyond those in standard pure tone audiometry. Over-air frequencies used (no bone testing) are 9, 10, 11.2, 12.4, 14, and 16 kHz. If both masked and unmasked results are available for the same visit, date, ear, and frequency, the masked results will be used for analysis. This test will be performed at Screening, Day 15, 60, 90, 150, and 210.

Baseline scores for analysis will be computed from the Screening visit. For measurements post-Screening, missing response values for a given frequency with classification of "NR" (no

response due to subject audiometric thresholds greater than the maximal calibrated dB of the equipment), will be imputed using the maximum dB for the audiometry equipment of a given site plus 5 dB and classified as no signal at that frequency. Missing response values at Screening will remain missing.

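### Pure-tone audiometry is modelled only as raw thresholds: mean dB change from Screening is never estimated, and the ear's own baseline is in no model

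*SAP*

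**What the plan says.** Protocol 7.2 lists the efficacy endpoints under "Mean changes from Screening in", and standard pure tone audiometry (air and bone) stands there beside WR and WIN. EHFA is listed the same way as an additional exploratory endpoint. Protocol 14.1.5 says of the descriptive analysis: "Calculations will include the observed data at each timepoint, and if relevant, the change from baseline". Of the models it says: "When appropriate, models will include adjustments for baseline as well as the stratification factors used at randomization".

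The SAP takes Screening as the audiometry baseline (7.5, 7.6) but does not carry it into the continuous models:

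- **7.5.1:** "treatment group comparisons for AC hearing threshold at each frequency will be analyzed using separate mixed-effect, repeated measures models", repeated for bone conduction.
- **7.5.5:** "treatment group comparisons for mean overall PTA will be analyzed using a mixed-effect, repeated measures model using fixed covariates for treatment group", with baseline WR stratum (below 50% or not), etiology, visit and visit-by-treatment as the remaining terms. BCA is handled the same way.
- **7.5.6 and 7.5.7** (low and high AC means) and **7.6.5** (EHFA mean) refer back to 7.5.5. **7.6.1** refers back to 7.5.1.

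Change in threshold is compared between arms only in dichotomised form: the 10 dB and 15 dB responders (7.5.2 to 7.5.4, with an optional GEE, and their EHFA counterparts in 7.6.2 to 7.6.4) and the composite, for which "treatment group comparisons for the composite endpoint will be analyzed using a logistic regression model" (7.5.9). Shifts in PTA category and air-bone imbalance are tabulated only. SAP Section 11 lists one change from the protocol, the dropped multiplicity adjustment.

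**The concern.** WR, WIN, TFI, HHIA and HSI all have a continuous change from baseline with its own model (SAP 7.3.3, 7.3.4, 7.4.3, 7.4.4, 7.7.2, 7.8.2, 7.9.2). Audiometry alone has none, which looks like an omission rather than a choice. As written, the report would contain neither a within-arm mean dB change with its SD nor an LS mean difference in change, although the protocol names that quantity.

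The second loss is precision. Eligibility admits a PTA anywhere from 26 to 70 dB, in ears selected for stable hearing loss. Most of the variance of a follow-up PTA is then likely to be the ear's permanent level, which Screening has already measured. A model without it leaves that variance in the error term. With 24 per arm, a moderate shift becomes much harder to see than the collected data allow. The binary WR stratum is a different measure, and the protocol asks for baseline in addition to the stratification factors.

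**Working it through.** The plan gives no SD, retest correlation or target difference, and it says the 24 per group has no formal statistical basis. There is therefore no figure of the plan's to reproduce. What follows compares two analyses of the same data, for PTA only.

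**Inputs**

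- n = 24 per arm, and 72 for pooled FX-322 (protocol 8.1; SAP Section 3).
- Raw SD s: assumed 9 to 12.7 dB. The upper value is a uniform spread over the eligible range: (70 − 26)/√12 = 12.7.
- SD of change c: assumed 3 to 6 dB.
- A true difference of 5 dB, for illustration only.

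**Formulas** (single visit, normal quantile)

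- Screening to follow-up correlation: r = 1 − c²/(2s²)
- SD adjusted for own baseline: s√(1 − r²)
- Half-width, 24 v 24: 1.96 × SD × √(2/24)

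**Half-widths and nominal power for 5 dB, 24 v 24**

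| s | c | r | Raw half-width | Adjusted half-width | Ratio | Raw power | Adjusted power |
|---|---|---|---|---|---|---|---|
| 9 | 3 | 0.944 | 5.09 | 1.67 | 3.04 | 49% | >99% |
| 9 | 4.5 | 0.875 | 5.09 | 2.47 | 2.07 | 49% | 98% |
| 9 | 6 | 0.778 | 5.09 | 3.20 | 1.59 | 49% | 86% |
| 12.7 | 3 | 0.972 | 7.19 | 1.69 | 4.26 | 28% | >99% |
| 12.7 | 4.5 | 0.937 | 7.19 | 2.51 | 2.87 | 28% | 97% |
| 12.7 | 6 | 0.888 | 7.19 | 3.30 | 2.18 | 28% | 84% |

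For example, with s = 9 and c = 6: r = 1 − 36/162 = 0.778; adjusted SD = 9 × √(1 − 0.605) = 5.66; half-width = 1.96 × 5.66 × 0.2887 = 3.20 dB.

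**Pooled FX-322 v placebo.** With √(1/72 + 1/24) in place of √(2/24), the half-width is 4.2 to 5.9 dB raw and 1.4 to 2.7 dB adjusted.

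**If the strata already help.** Suppose WR stratum and etiology explain 30% of PTA variance, so s becomes s√0.7 with c unchanged. The ratio is then 1.4 to 3.6. Raw power is 37% to 63%, and adjusted power at least 85%.

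**By correlation alone.** The ratio is 1/√(1 − r²): 1.40 at r = 0.7, 2.03 at 0.87 and 2.93 at 0.94.

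**Bias check.** In 20,000 simulated trials (24 v 24, s = 12.7, r = 0.9, true difference −5 dB), the raw, change and baseline-adjusted estimates all averaged −4.99 dB. Their empirical SEs were 3.69, 1.63 and 1.61 dB. Chance imbalance at Screening between the two arms exceeded 5 dB in 18% of trials, and the raw contrast carries most of it.

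**The case against.** **Change is not wholly absent.** Threshold change does enter the responder models and the composite, and arm mean change could be had by subtracting visit means if Screening is tabulated. But a dichotomised change is not a mean change, and subtraction gives no SD, interval or contrast. The responders are also a poor substitute as written. SAP 7.5.2 has the flag "computed as 1 if the post-baseline threshold – baseline threshold is" at least 10 dB, and for a threshold a rise is worsening. That is a separate error, to be corrected on its own account.

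**Screening may be a repeated level.** This is the strongest point. The SAP does not say which visits enter the model. If Screening is one of them, a visit-by-treatment contrast against Screening is the difference in mean change. Its half-width of 1.96 × c × √(2/24) is 1.7 to 3.4 dB, nearly all of the available gain. But no such contrast is specified. The specified by-visit LS mean differences would still be raw comparisons, with the wide intervals shown above.

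**The assumed range is favourable.** At r = 0.7 the adjusted half-width is 3.6 to 5.1 dB, and power for 5 dB is 77% (s = 9) or 48% (s = 12.7). Those cases need a change SD of 7.0 to 9.8 dB, outside the range assumed here. The gain is then smaller, but in the same direction.

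**Baseline is not a covariate for WIN or the questionnaires either.** This is true. Those measures do have a change-score model, however, so their named endpoint is estimated and most of the between-subject level is removed.

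**The protocol's wording is permissive and the study exploratory.** The protocol qualifies its baseline adjustment, there is no primary endpoint, and p-values are descriptive. This limits the severity. The endpoint itself carries no such qualifier.

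**Conclusion.** The concern holds and should be fixed. The protocol's mean-change endpoint for pure tone audiometry, and likewise for EHFA, is not estimated by any specified continuous analysis, and Section 11 does not declare this.

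There is no bias: the raw comparison is centred correctly over randomisation and its intervals have valid coverage. The cost is precision. Under the assumed SDs the raw interval for a PTA comparison of one arm with placebo is 1.6 to 4.3 times as wide as it need be, or 1.4 to 3.6 times if the strata explain 30% of the variance. The size rests on assumed SDs that the documents do not give; the direction does not. No figure is claimed for EHFA or for single frequencies.

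**What to change.** For PTA, BCA, the low and high AC means and each AC and BC frequency:

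1. Define dB change from Screening and summarise it by visit and arm.
2. Fit the MMRM to post-Screening change. Add the ear's continuous Screening value of that measure, and its interaction with visit, to the existing stratification terms.
3. State that Screening is not a repeated level in that model.

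Apply the same to EHFA once the rule for no response at Screening is settled. If raw thresholds are to remain the only continuous analysis, declare the departure in Section 11. WR, WIN, TFI, HHIA and HSI need no change on this point.

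The cost is SAP wording, model code and one set of change tables; Screening thresholds are already collected. There is one real price. Under both 7.5 and 7.6, "Missing response values at Screening will remain missing", so an ear with no response at Screening has no baseline and drops out of the change model at that frequency. This could matter most for EHFA, which is why that part waits.
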